### 8.2 Randomization, blinding and treatment allocation

Patients who meet the inclusion criteria (see paragraph 4.2) can be included in the study after consultation with the radiation oncologist and after they have signed informed consent. They will be randomized into either of the two cohorts.

Blinding of the groups cannot be performed, because the planning system needs to calculate the treatment time based on the fractionation schedule, which is determined by randomization. The involved employees of the radiation department need to process the data in the radiation therapy software and they need to carry out QA checks on the radiation treatment plans. The latter can only be performed if all information is available.

[figure not shown]
Patients who are randomized into the standard treatment group will receive the treatment as currently advised by the LPRNO guidelines. Patients will receive 1 fraction of SRT, unless it concerns a large tumor in proximity to the brainstem or a large tumor in proximity to other metastases, see paragraph 8.3.3. Based on previous literature, local progression or survival outcome are comparable for SRT in 1 or 3 fractions.

Randomization to either SRS (1 or 3 fractions, see paragraph 8.3.3) or fSRT (5x7Gy or 5x6 Gy if in brainstem, see paragraph 8.3.3) will be 1:1, stratified by institute with block sizes 4 and 6.

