### 8.3.5 SRT PTV

The PTV is defined by a 0-2 mm isotropic expansion of the GTV, according to institutional standards for SRT. If a brain metastasis is within or adjacent to the brainstem, the PTV margin will be 0 mm. If in an institution a smaller GTV to PTV margin is used when lesions are treated using multiple isocenters, then this technique is to be considered to reduce the V12Gy of the largest brain metastasis if it would otherwise be more than 10 cm^3.

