## 10. STATISTICAL ANALYSIS

### 10.1 Primary study parameter(s)

Differences in the composite endpoint (either radionecrosis or local failure) at 2 years post-radiotherapy are calculated as a percentage in each cohort. The binomial test will be used to compare the percentage between the two cohorts.

Summary tables for continuous variables will include the following statistics: mean, standard deviation. Summary tables for categorical variables will include: N, proportion.

If the data is normally distributed, the means will be compared using independent samples Student's T-Tests. In case of violation of the normality assumptions, non-parametric tests will be used. Proportions will be compared by using Chi-square testing. Unless otherwise indicated, tests will be 2-sided.

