### 10.2 Secondary study parameter(s)

Secondary study parameters (as listed in paragraph 8.1.2, including facultative endpoints such as HRQoL and neurocognition) will be presented per cohort. Due to the presence of repeated measurements mixed modelling will be used to analyze use of anti-epileptica, dexamethasone and bevacizumab, IADL and to investigate the effect of fSRT on quality of life.

Overall survival (from date of first radiotherapy until death) will be estimated by using Kaplan-Meier methodology. To assess whether there is difference between survival in the groups, the Log-rank test will be used. To investigate the effect of prognostic factors on survival, a Cox regression model will be used. To estimate the cumulative incidence of adverse local events (ALE), a competing risk model with death as a competing risk will be estimated. Fine and Gray's test will be employed to assess the difference between cumulative incidence in the two cohorts. Cause specific hazard Cox model will be employed to investigate the effect of prognostic factors on the cumulative incidence of ALE.

Care will be taken to minimize missing data and to continue to follow up those who withdraw from the study. To account for non-compliance and protocol deviation the analysis will be performed based on the intention to treat concept.

All analyses concerning the competing risk model will be performed in R environment by using the library mstate and cprisk. All other analyses will be performed in SPSS version 26.0 (IBM Corp, Armonk, NY).

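### Randomisation is stratified by institute, but the primary and time-to-event tests are named without it: a conservative and usually small mismatch that is cheap to correct

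*Protocol*

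**What the plan says.** Protocol section 8.2 fixes the allocation: randomisation "will be 1:1, stratified by institute with block sizes 4 and 6".

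Section 10.1 fixes the primary comparison of the ALE percentage (radionecrosis or local failure at 2 years): "The binomial test will be used to compare the percentage between the two cohorts". It adds, for proportions in general: "Proportions will be compared by using Chi-square testing".

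Section 10.2 fixes the time-to-event comparisons. For survival: "To assess whether there is difference between survival in the groups, the Log-rank test will be used". For ALE with death as competing risk: "Fine and Gray's test will be employed to assess the difference between cumulative incidence in the two cohorts". Covariates enter only through models for prognostic factors, which are not listed: "To investigate the effect of prognostic factors on survival, a Cox regression model will be used".

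Institute does not appear in section 10 as a stratum, covariate or random effect. The sample size in section 4.4 also rests on an unstratified test, a pooled-variance Z test evaluated exactly.

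**The concern.** Blocked randomisation within institute keeps the arms nearly balanced in every institute, so differences between institutes largely cancel out of the arm difference. A test that pools the institutes still counts those differences as error. If institutes differ in ALE risk, its standard error is too large, its true level falls below 5%, and it forgoes some of the precision that the stratified design makes available.

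The protocol gives reasons why institutes might differ. Section 8.3.5 leaves the margin to the centre: "The PTV is defined by a 0-2 mm isotropic expansion of the GTV, according to institutional standards for SRT". Fixation and position verification also follow local practice (8.3.6, 8.3.7). Radionecrosis is called by a dedicated radiologist or board (8.1.1), with no central reading stated. Planned power is 0.8051, so there is little reserve, and the trial is open label. That makes it worth settling before the data are seen whether the leading result is the adjusted or the unadjusted one.

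**Working it through.** **Inputs from the protocol.** 59 patients per arm, 118 in total; ALE risk 30% v 10%; two-sided alpha 0.05; pooled-variance Z test (4.4, 10.1). Blocks of 4 and 6 within institute (8.2). The two risks are labelled as 1-year values in 4.4 and serve here only as planning values.

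**Assumed, because the protocol gives neither:** the number and size of institutes, and the spread of ALE risk between them.

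**Step 1: the plan's own figure.** Enumerating two independent binomials with n = 59 and rejecting when |Z| ≥ 1.96 gives power 0.8051 at 30% v 10%, and level 0.0507 at a common 10%. Both match section 4.4. The uncorrected chi-square statistic is Z², so the result is the same if the chi-square test of 10.1 is used.

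**Step 2: the expected size of the effect.** Let p be the overall risk and V the variance of the institute risks. The pooled test works with p(1−p) per patient. With balance inside institutes, the true variance of the difference corresponds to p(1−p) − V. So

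R = 1 − V / [p(1−p)], and true level ≈ 2[1 − Φ(1.96/√R)].

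- Three equal institutes at 10/30/50%: p = 0.30, p(1−p) = 0.21, V = (0.04 + 0 + 0.04)/3 = 0.0267, R = 0.873, 1.96/√R = 2.098, level ≈ 3.6%.
- Four equal institutes at 15/25/35/45%: V = (2×0.0225 + 2×0.0025)/4 = 0.0125, R = 0.940, 1.96/√R = 2.021, level ≈ 4.3%.
- Institutes of 78/20/20 patients at 30/10/50%: V = (40/118)×0.04 = 0.0136, R = 0.935, 1.96/√R = 2.026, level ≈ 4.3%.

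**Step 3: simulation.** 118 patients, blocks of 4 and 6 within institute, pooled Z v Cochran-Mantel-Haenszel (CMH) without continuity correction, about 6,000-8,000 trials per row. Treatment odds ratio common to all institutes. Percentages are unstratified v stratified. Where two pairs appear, they are for 3 and for 6 equal institutes.

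| Assumed institutes | Type I error | Power |
|---|---|---|
| No difference | 5.1 v 4.9; 5.4 v 5.2 | 80.4 v 79.5; 80.0 v 79.3 |
| Log-odds SD 0.5 | 4.6 v 4.8; 5.0 v 5.2 | 80.5 v 80.9; 80.6 v 80.9 |
| Log-odds SD 1.0 | 4.1 v 5.3; 3.6 v 4.5 | 81.6 v 84.5; 82.0 v 84.5 |
| Log-odds SD 1.5 | 2.9 v 5.0; 2.8 v 5.5 | 83.1 v 88.0; 82.8 v 88.3 |
| Three equal, 10/30/50% | 3.8 v 4.9 | 80.5 v 82.2 |
| Four, 15-45% | 4.4 v 4.9 | 80.4 v 80.9 |
| Six, 10-60% | 3.6 v 5.0 | 80.6 v 83.1 |
| 78/20/20 patients, 30/10/50% | 4.6 v 5.1 | 80.8 v 81.3 |
| 78/20/20 patients, 30/15/45% | 4.5 v 4.8 | 80.7 v 80.8 |

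Simulation error with 6,000 trials is √(0.05×0.95/6000) = 0.3 points for a level and √(0.8×0.2/6000) = 0.5 points for a power. The levels agree with step 2 within that error.

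The SD 1.5 row is an outer bound. With three institutes and a mean standard-arm risk of 30%, the log-odds are −1.27 and −1.27 ± 1.84, which means institute risks of about 4%, 22% and 64%.

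**Not computed.** The effect on the log-rank and Fine and Gray tests, because the protocol gives no survival inputs by institute.

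**The case against.** **The primary test is the type that sized the trial.** Sections 4.4 and 10.1 are consistent with each other on this. A reader might infer that planned power is lost. It is not: unstratified power is about 80% or higher in every scenario, and only a possible gain is forgone. This objection stands.

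**There is no validity error.** A reader might infer that the p-values are unsafe, or that reported intervals do not match the design. The error runs only in the conservative direction. Sections 10.1 and 10.2 specify no interval for a treatment comparison, so there is none to call mismatched. This also stands.

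**The size depends on assumed spreads.** If one hospital dominates, the gain is 0.1-0.5 points. That is plausible, because section 4.4 argues feasibility from a single hospital with about 135 eligible patients a year, but the protocol gives no split between centres.

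**The margin is weak evidence of an ALE difference.** A spherical 8 cm³ GTV (radius 1.241 cm) becomes a PTV of 8.0, 10.1 or 12.5 cm³ at 0, 1 or 2 mm, and so crosses the 10 cm³ row of the dose table in 8.3.3. But that table varies dose by PTV only in the standard arm. The example therefore shows a one-arm dose difference, a treatment-by-institute interaction that the simulation does not model. It does not show that ALE risk differs, since ALE combines local failure and radionecrosis, which dose may move in opposite directions.

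**The SAP may stratify.** It is not shown, and nothing in section 10 forbids stratification. This stands only in part: the protocol does name each test, so a stratified primary test is better fixed in 10.1 than left to another document.

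**Conclusion.** The point holds as one of efficiency and consistency, not validity. The design stratifies by institute, and the named primary, log-rank and Fine and Gray tests do not. If institutes differ markedly in ALE risk (10/30/50%, 10-60%, or log-odds SD 1.0), the primary test runs at about 3.6-4.1% instead of 5% and forgoes about 1.7-3.0 points of power. A still wider spread (SD 1.5) would give about 2.8-2.9% and 5-6 points, but needs institute risks that are hard to credit. With a spread of 15-45%, or one dominant institute, the power difference is about half a point or less. With no spread, stratifying loses 0.7-0.9 points. All of this rests on assumed numbers of institutes, assumed spreads and a common odds ratio. For the two tests in 10.2 the argument is one of principle, and its size is unknown.

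**What to change.** In 10.1, name the primary comparison as a two-sided Cochran-Mantel-Haenszel test stratified by institute, and report the Mantel-Haenszel risk difference with its 95% CI. State before the data are seen how institutes below a set minimum size are pooled, since an institute with one arm only, or with no events, contributes nothing to the test. Keep the unstratified test as a sensitivity analysis.

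In 10.2, stratify the log-rank and cumulative incidence tests by the same pooled institutes, for consistency with the primary analysis.

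If the unstratified tests are kept as the main analysis, say so and give the reason.

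Cost: two or three sentences, no new data and no change to the sample size. The statistical price is under one point of power if institutes do not differ at all.

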### 10.2 Secondary study parameter(s)

Secondary study parameters (as listed in paragraph 8.1.2, including facultative endpoints such as HRQoL and neurocognition) will be presented per cohort. Due to the presence of repeated measurements mixed modelling will be used to analyze use of anti-epileptica, dexamethasone and bevacizumab, IADL and to investigate the effect of fSRT on quality of life.

Overall survival (from date of first radiotherapy until death) will be estimated by using Kaplan-Meier methodology. To assess whether there is difference between survival in the groups, the Log-rank test will be used. To investigate the effect of prognostic factors on survival, a Cox regression model will be used. To estimate the cumulative incidence of adverse local events (ALE), a competing risk model with death as a competing risk will be estimated. Fine and Gray's test will be employed to assess the difference between cumulative incidence in the two cohorts. Cause specific hazard Cox model will be employed to investigate the effect of prognostic factors on the cumulative incidence of ALE.

Care will be taken to minimize missing data and to continue to follow up those who withdraw from the study. To account for non-compliance and protocol deviation the analysis will be performed based on the intention to treat concept.

All analyses concerning the competing risk model will be performed in R environment by using the library mstate and cprisk. All other analyses will be performed in SPSS version 26.0 (IBM Corp, Armonk, NY).

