### 8.3.6 SRT planning procedure

Patients will be immobilized in supine position wearing a thermoplastic mask or stereotactic non-invasive frame, with or without bite block and/or other fixation, according to institutional standards for SRT. The accuracy of the stereotactic fixation system should be sufficient to justify the CTV to PTV margin used. This means the intrafraction motion should at least be within the CTV-PTV margin used. If a margin of 0 mm is used, the maximum intrafraction motion should be <0.5 mm, with the SD being less than 0.25 mm. A planning CT scan with

≤2 mm thick contiguous slices (preferable CT slice thickness = 1mm) will be fused to a contrast-enhanced stereotactic MRI scan. The interval between the planning-MRI and actual SRT treatment is a maximum of 3 weeks.

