### **8.5 Replacement of individual subjects after withdrawal**

With respect to patients applicable for this study willing to participate, and who have signed informed consent (paragraph 11.2): before randomization any patient will be replaced if the patient withdraws for any reason. These patients are not included in the statistical analysis. After the randomization, patients withdrawing for any reason will not be substituted by additional patients and these patients are analyzed by intention to treat.

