#### 9.2.2 Serious adverse events (SAEs)

A serious adverse event is any untoward medical occurrence or effect that

- results in death;
- is life threatening (at the time of the event);
- requires hospitalization or prolongation of existing inpatients' hospitalization;
- results in persistent or significant disability or incapacity;
- is a congenital anomaly or birth defect; or
- any other important medical event that did not result in any of the outcomes listed above due to medical or surgical intervention but could have been based upon appropriate judgement by the investigator.

An elective hospital admission will not be considered as a serious adverse event.

The investigator shall report serious adverse events to [[contact]](mailto:[contact]) without undue delay after obtaining knowledge of the events, unless, for certain serious adverse events, the protocol provides that no immediate reporting is required.

Adverse experiences of a serious and unexpected nature, whether or not related to the cerebral radiotherapy, must be reported immediately. Adverse events that are

unexpected, should be reported if there is a possibility that it could be related to the administration of the radiotherapy.

The investigator will report all SAEs to the sponsor without undue delay after obtaining knowledge of the events, except for the following SAEs: epilepsy, deterioration of existing neurologic impairment after the radiotherapy, alopecia, fatigue, headache, and taste disorders.

The sponsor will report the unexpected SAEs through the web portal *ToetsingOnline* to the accredited METC that approved the protocol, within 7 days of first knowledge for SAEs that result in death or are life threatening followed by a period of maximum of 8 days to complete the initial preliminary report. All other unexpected SAEs will be reported within a period of maximum 15 days after the sponsor has first knowledge of the serious adverse events.

Patients with brain metastases generally have a poor life expectancy of around 3-12 months. Therefore, a significant proportion of patients is expected to die within the study duration of 1 year after SRT.

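### Overall survival starts at the first radiotherapy, so a randomised patient who never receives any has no survival time, although intention to treat is promised

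*Protocol*

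**What the plan says.** Section 10.2 defines the time origin in its sentence on survival: "Overall survival (from date of first radiotherapy until death) will be estimated by using Kaplan-Meier methodology". The arms are then compared: "To assess whether there is difference between survival in the groups, the Log-rank test will be used". The same section gives the analysis principle: "To account for non-compliance and protocol deviation the analysis will be performed based on the intention to treat concept".

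Section 8.5 applies that principle to losses after allocation: "patients withdrawing for any reason will not be substituted by additional patients and these patients are analyzed by intention to treat". Section 8.6 adds that withdrawn patients are asked whether their chart may be consulted, among other things for length of survival.

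On the order of events, section 8.2 randomises patients after signed consent and explains why blinding is impossible: "the planning system needs to calculate the treatment time based on the fractionation schedule, which is determined by randomization". Section 8.1.2 lists survival as a secondary endpoint and ties its two-year value to the time since SRT. Section 2 names estimation of overall survival, and of the cumulative incidence of local failure or radionecrosis with death as competing risk, among the secondary objectives.

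**The concern.** An intention-to-treat comparison needs a starting point that every randomised patient has. The date of first radiotherapy is not one: it occurs after randomisation, and only treated patients have it. A patient who receives no fraction at all has no survival time as defined, even if the date of death is known from the chart. Read literally, 10.2 therefore compares treated patients, while 8.5 and the last part of 10.2 say that all randomised patients are analysed.

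The origin can also depend on the arm. Allocation is known to patient and physician, and the experimental schedule needs five visits against one or three. If losses or waiting times before the first fraction differed between arms, the survival contrast would no longer be fully protected by randomisation.

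The competing-risk analysis of adverse local events in 10.2 states no origin. If it took over the survival origin, deaths before treatment would be missing there as competing events too.

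**Working it through.** **1. The rules side by side.**

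- Start of overall survival (10.2): date of first radiotherapy.
- Who is analysed (8.5 and 10.2): patients as randomised, including those who withdraw after randomisation.
- Order (8.2): signed consent, then randomisation, then a plan specific to the allocated schedule, then the first fraction. Every patient therefore has some interval between randomisation and first fraction.
- Start date for a randomised patient without any fraction: none is given in any section.

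For such a patient the first two rules cannot both be followed. This part needs no arithmetic.

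**2. The plan's own figures.** No events, power or sample size are given for survival. The only design calculation, in 4.4, is for the primary endpoint. Exact enumeration of the pooled Z test at 30% versus 10% with 59 per arm gives power 0.8051 and actual alpha 0.0507, both as stated. The total is 118 × 1.10 = 129.8, stated as 130. Only the 130 is used below.

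**3. How many patients might die before the first fraction.**

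Inputs:

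- N = 130 (4.4).
- Life expectancy (9.2.2): "Patients with brain metastases generally have a poor life expectancy of around 3-12 months". This is read here as a median, with a constant hazard (assumption); 6 months is added as an intermediate value.
- Gap *t* from randomisation to first fraction: not stated anywhere. Assumed to be 1 week, with 2 and 3 weeks shown for range.

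Formula: proportion dying in the gap = 1 − 0.5^(t / median), with 30.44 days per month. Expected number = 130 × proportion.

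Example, 1 week and 12 months: t = 7 / 30.44 = 0.230 months; 1 − 0.5^(0.230 / 12) = 1.3%; 130 × 0.0132 = 1.7.

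| Median survival | 1 week | 2 weeks | 3 weeks |
|---|---|---|---|
| 12 months | 1.3% (1.7) | 2.6% (3.4) | 3.9% (5.1) |
| 6 months | 2.6% (3.4) | 5.2% (6.7) | 7.7% (10.0) |
| 3 months | 5.2% (6.7) | 10.1% (13.1) | 14.7% (19.2) |

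With the 1-week gap and a median of 6 to 12 months, the result is 1.7 to 3.4, or about 2 to 3 of 130. Patients who decline or withdraw and never receive radiotherapy would add to this; the protocol gives no rate for them.

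**The case against.** The strongest reply is that the protocol nowhere excludes these patients. Section 8.5 keeps withdrawals in the analysis, 8.6 seeks their length of survival, and 10.2 promises continued follow-up. A convention for a rare missing start date could be left to the statistical analysis plan. Survival is secondary and unpowered. This limits the weight of the point but does not remove it: the protocol is not silent on the origin but states one, and a later plan that follows it inherits the conflict.

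Several stronger readings are tempting, and the documents do not support them.

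- *All planning follows randomisation.* Section 11.2 lets planning start at oral consent, so some preparation may come first. Only the schedule-specific plan must follow allocation.
- *The gap is up to three weeks, so up to 19 patients are lost.* Section 8.3.6 says: "The interval between the planning-MRI and actual SRT treatment is a maximum of 3 weeks". That limits planning MRI to treatment, not randomisation to treatment. The figure of 19 also needs that maximum for every patient and the shortest life expectancy, whereas section 4.2 requires a Karnofsky score of at least 70 and suitability for SRT. It is an extreme upper bound.
- *Anyone who refuses the allocated schedule is lost.* A patient who takes the other schedule still has a date of first radiotherapy. Only patients who receive none are affected.
- *Survival is overstated.* Under the constant hazard used above, a curve started later is unchanged. Overstatement requires that those lost are frailer than the rest, which is plausible but assumed.
- *The comparison is biased.* Nothing says that the first fraction comes later, or that refusal is more common, in either arm. Needing five slots does not by itself delay the first one.

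**Conclusion.** The inconsistency is real and should be corrected. Section 10.2 fixes an origin that only treated patients have, while 8.5 and 10.2 promise analysis of all randomised patients, and nothing in the protocol resolves this for a patient who receives no radiotherapy. That conclusion rests on the text alone.

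The effect is probably small: about 2 to 3 of 130 deaths before treatment, assuming a one-week gap, a constant hazard and a median of 6 to 12 months, plus an unknown number of other patients who never start. Differential loss between the arms is a risk of an open-label design with unequal visit burden, not a demonstrated bias. The primary endpoint's sample size is unaffected.

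**What to change.** In 10.2, define overall survival *from date of randomisation until death* for all randomised patients, whether or not radiotherapy is given. Align the survival endpoint in 8.1.2 with the same origin; changing 10.2 alone would leave the two sections in conflict. The first-radiotherapy origin may be kept as a sensitivity analysis.

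For the competing-risk analysis of adverse local events, state the origin and ensure that deaths of randomised patients before treatment are counted as competing events. The MRI calendar and the primary endpoint at two years after radiotherapy can stay tied to SRT.

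The cost is a short change of wording in two sections and a statement of the competing-risk origin. Every randomised patient has a randomisation date, and no stated sample-size figure moves. The downside is that the survival time of each treated patient lengthens by the interval from randomisation to first fraction, which matters when comparing with series timed from treatment; the sensitivity analysis covers that.
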